Secondary outcome measures to assess recovery are the Patient Reported Outcomes Measurement Information System (PROMIS) Mobility (M) and Pain Interference (PI) domains. PROMIS is a general measure of health administered over particular health domains. This instrument has been tested extensively and is reliable and precise.⁴⁵ Scores range from 0-100 and are normalized so that a score of 50 is the population mean, with 10 points representing a standard deviation is 10 points. For the Mobility domain larger scores represent more function; for the PI domain larger scores represent more pain. The instrument administered via computer-adaptive testing (CAT) to minimize question burden. The Scoliosis Research Society 22 (SRS-22) will be used in assessing the quality of life in AIS patients. The SRS-22r includes 22 items distributed among five different factors (pain, self-image/appearance, function/activity, mental health, and satisfaction with management). Each component includes five items, except for the “satisfaction with management”, which only contains two items. Secondary measures to assess the anti-inflammatory effect of lidocaine will be serum levels of IL-10, IL-4 and IL-12.

The anticipated outcome is decreased in-hospital opioid consumption for those patients treated with intravenous lidocaine. Other anticipated outcomes are decreased opioid consumption at three-months after surgery, with improved recovery as measured by PROMIS-M and PROMIS-PI measures at 6 weeks, 3 months, 6 months, and 12 months after surgery. We anticipate that the anti-inflammatory effect of lidocaine will reflect a smaller postoperative inflammatory response as measured by IL-10, IL-4, and IL-12.

G Statistical Plan

G1 Sample Size Determination and Power

The target sample size of 50 patients, 25 per group, is based upon a two-tail test at the 0.05 level of significance, with 80% power to detect an effect size of $d=0.8$. Prior data from our institution has shown an average postoperative morphine-equivalent consumption of 149 mg with a standard deviation of 37 mg. The proposed effect size is equivalent to approximately a 20% reduction in postoperative morphine-equivalent opioid consumption. The primary outcome measure is the inpatient measure of postoperative opioid consumption. As such, loss-to-followup is not possible, though 25 per group accounts for 10% loss due to treatment noncompliance which is unlikely.

G2 Analysis Plan

General Analysis Strategy: Our approach to data analysis includes three consecutive stages. Most analyses will be performed using SAS software, which

Intravenous Lidocaine to Reduce Postoperative Opioid Consumption and Improve Recovery After Posterior Spinal Fusion for Adolescent Idiopathic Scoliosis

has a wide range of statistical routines and offers great flexibility in data manipulation.

Descriptive Analysis and Data Reduction:

Quality control will be ongoing throughout the project, as part of data management procedures that monitor data quality at each site and overall. However, prior to analysis, the data will be fully examined to confirm data quality and make final corrections. After addressing data quality, each variable will be summarized via marginal distributions as well as by relevant separate and combined study factors [(e.g., treatment, crossover status, patient demographics (age, gender, race)], and clinical factors (e.g., curve type, curve magnitude, etc.)]. Distribution summaries for continuous variables will include means, medians, interquartile ranges, minima and maxima and standard deviations; those for categorical variables will include proportions and 95% confidence intervals. The amount and patterns of missing data will be examined early and regularly during data collection to detect possible problems with instrument completion. Prior to analysis the amount and patterns of missing data are also important to see whether adjustments will be needed at the Inferential Analysis Stage. Those who complete data collection will be compared with those who drop out before the end of follow-up to identify potential selection biases, causing the study pool to differ from the target population. Transformations will be employed as needed to produce variables that conform to the distributional assumptions underlying the regression models that will be used.

After 10 patients have completed the study, immunophenotyping with flow and mass cytometry will be performed to confirm appropriate data are collected with the chosen panels.

H Data Handling and Record Keeping

H1 Confidentiality and Security

The primary data will come from the information contained in the patient's medical records related to their illness. In order to extract the relevant information, study staff will review the data from their records and record it into a secure database. Only the minimum necessary data will be looked at and recorded for the study. Records will be stored behind secured firewalls maintained by Washington University and is compliant with FDA Code of Federal Regulations Title 2, Volume 1, CITE: 21CFR11 and include the use of: (1) uniqueness of individual log in with restricted access via a strong username and password policy, (2) ability for users to periodically modify identification codes or passwords, (3) secure, computer-generated time-stamped audit trails, (4) 128-bit Secure Socket Layer (SSL) encryption for transactional safeguarding (5) electronic de-authorization of lost, stolen, or missing user authorization codes. Only study staff will have password access. There will be no patient identifiers or information that could link the patient to any published material.

Any paper records will be maintained in locked file cabinets in code-accessed suites.

H2 Case Report Forms and Source Documents

Using the assigned patient ID code, the WU coordinator will enter all eCRF patient data into the study REDCap secure database. The eCRF will be completed by the principal investigator or his designee. If any entry on a source document requires a change, a single line will be drawn throughout the incorrect entry, and the correction will be entered in ink, initialed and dated. Whiteout, erasures, or obliteration on source data are not permitted. The primary data will come from the information contained in the patient's medical records related to their illness. In order to extract the relevant information, study staff will review the data from their records and record it into a secure database. Only the minimum necessary data will be looked at and recorded for the study.

H3 Records Retention

We will retain identifiers indefinitely on patients who consent to participate in this study. This will be done to protect the integrity of our study and for potential use in future, IRB-approved research.

I Study Monitoring, Auditing, and Inspecting

I1 Study Monitoring Plan

After the first 15 patients are enrolled, a group consisting of the Principal Investigator and an unengaged physician will review the AE/SAE data. The data will be reviewed blinded. If intraoperative surgical, medical, or anesthetic complications occur, including cardiac arrhythmia, the study medication will be stopped and the patient withdrawn from the study. The patient will be analyzed in an intent-to-treat analysis, though they will be excluded from as-treated analyses. After surgery, patients will be seen and examined twice daily with attention to postoperative complications. As the study-drug will have completed infusion, all complications will be recorded though patients will remain enrolled in the study and analyzed per-protocol.

Special attention will be given if adverse events occur in a higher frequency than expected given patient age and health condition. Serious adverse events, or those that are life threatening, result in death, prolonged hospitalization, readmission, cause persistent disability or require urgent intervention to prevent permanent morbidity will be monitored for up to 30 days after the drug is administered. If there appears to be an imbalance in AE/SAE, unblinding and analysis will ensue to determine if the study should continue. Early termination will occur if SAEs are linked to the treatment arm.

After 10 patients have completed the hospital phase of the study, flow and mass cytometry will be performed to ensure we are capturing cell types and signaling proteins as anticipated.

All protocol violations and SAE's will be reported to HRPO within the WU HRPO policies and procedures reporting guidelines
SAEs will be tracked through resolution.

J References

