- a. Determine changes in leukocyte frequencies and phenotype during and following surgery by flow cytometric immunophenotyping.
- b. Assess systemic cytokine responses during and following surgery with and without IV lidocaine treatment.
- c. Define surgery- and lidocaine-induced functional changes in immune cell populations by mass cytometry.

C2 Secondary Aims

To determine the effectiveness of systemic lidocaine to improve recovery after posterior spinal fusion for AIS. We hypothesize that patients receiving intravenous lidocaine will experience faster recovery from surgery. To test this hypothesis PROMIS-Computer Adaptive Tests (CAT) for Mobility (M) and Pain Interference (PI) will be compared between groups at enrollment, 6 weeks, 3 months, 6 months, and 12 months after surgery. The Scoliosis Research Society 22 (SRS-22) will also be completed at these time points.

D Investigational Agent

D1 Clinical Data to Date

Lidocaine hydrochloride (2-Diethylamino-2', 6'-acetoxylidide monohydrochloride) is an amide-type, short-acting local anesthetic and delivered as an aqueous solution for intravenous administration. It has a half-life of 1.5-2 hours. A traditional method of administration is via epidural delivery. Epidural lidocaine is effective and this effect is due, in part, to systemic absorption. Systemic (intravenous) administration of lidocaine is a Food and Drug Administration approved method of delivery. Low plasma levels are needed for effective use, 0.5 μ g/mL to 5.0 μ g/mL. Given this low concentration required and the short half-life, continuous infusion of lidocaine is thought to be generally safe with low risk of complication.

The low plasma levels have not been associated with hemodynamic instability nor have they been associated with changes in cardiac contractility. No interactions with the autonomic nervous system have been reported and there are no known effects on sinoatrial conduction. Lidocaine is metabolized by the liver, with less than 10% excreted in urine. Complications are rare. Despite concerns for arrhythmias, intravenous lidocaine has been used in cardiothoracic

Intravenous Lidocaine to Reduce Postoperative Opioid Consumption and Improve Recovery After Posterior Spinal Fusion for Adolescent Idiopathic Scoliosis

surgery without increased rates of cardiac complications. Give this volume of evidence, we feel that intravenous lidocaine in the setting of AIS surgery is safe.

D2 Dose Rationale and Risk/Benefits

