Patients consenting to randomization will be randomized 1:1 to the control or study group. A permuted randomized block approach¹ with blocks of size 4, 6 and 8. Given the relatively large number of patients to be enrolled, no stratification will be performed. After 30 patients are enrolled, an interim analysis, without unblinding, of baseline covariates will be performed to ensure equal distribution between groups. If distribution is uneven for covariates concerning for confounding, then stratification by these covariates will be employed to ensure equal distribution with randomization.

Patient loss to follow-up can affect the randomization balance and quality. Aims 1a and 2 are in-hospital studies and outcome data will be collected during the hospital stay. Loss-to-followup is not expected during the hospital stay. Aims 1b and 3 may be affected by loss-to-followup. All efforts will be made to collect follow-up data. A scheduled spine clinic visit is the preferred method of data collection. If the patient will not attend clinic, then they will be contacted by mail, email, and/or phone. Surveys may be sent electronically for completion. At enrollment, the contact information for two family members not living with the patient will be obtained. These people will be contacted should contact with the patient be lost. Registered mail will be sent to the last known address, with a self-addressed, stamped return envelope to collect outcomes data. Administration of PROMIS-CAT and SRS are valid by telephone and email.⁴⁷

Intravenous Lidocaine to Reduce Postoperative Opioid Consumption and Improve Recovery After Posterior Spinal Fusion for Adolescent Idiopathic Scoliosis

2.d Risks and Benefits

E3 Study Drug

3.a Description

Lidocaine hydrochloride (2-Diethylamino-2', 6'-acetoxylidide monohydrochloride) is an amide-type, short-acting local anesthetic and delivered as an aqueous solution for intravenous administration. It has a half-life of 1.5-2 hours. A traditional method of administration is via epidural delivery. Epidural lidocaine is effective and this effect is due, in part, to systemic absorption. Systemic (intravenous) administration of lidocaine is a Food and Drug Administration approved method of delivery. Low plasma levels are needed for effective use, 0.5 μ g/mL to 5.0 μ g/mL. Given this low concentration required and the short half-life, continuous infusion of lidocaine is thought to be generally safe with low risk of complication.

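### The recovery aim lists enrollment as one of five PROMIS comparison times, and no baseline-adjusted or repeated-measures analysis is specified

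*Combined protocol and SAP*

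**What the plan says.** All references are to the combined protocol and SAP.

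- **C2 Secondary Aims.** The recovery hypothesis is to be tested on PROMIS Mobility and Pain Interference, which "will be compared between groups at enrollment, 6 weeks, 3 months, 6 months, and 12 months after surgery". SRS-22 is to be filled in at the same times; no group comparison of it is stated.
- **F2 and F4.** Benefit on PROMIS is anticipated at the four postoperative visits only; enrollment is not among them.
- **E2, 2.c Randomization Method and Blinding.** "Aims 1b and 3 may be affected by loss-to-followup". No rate is given, and neither label appears in the current list of aims. The surrounding text is about collecting PROMIS and SRS at follow-up, so it very probably means these outcomes. Several steps to retain contact with patients are listed.
- **G2 Analysis Plan.** Three stages are announced but only the descriptive one is written out. Regression models are mentioned without outcome, covariates or structure. Missing data will be inspected "to see whether adjustments will be needed at the Inferential Analysis Stage"; no method is named.
- **G1.** The only sample size is for opioid consumption: "The target sample size of 50 patients, 25 per group". No power statement exists for PROMIS or SRS-22.

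**The concern.** Listing enrollment among the comparison times gives the baseline the wrong job. A group comparison before treatment cannot inform the recovery question, because randomisation makes any difference a chance one. The same score, used as a covariate, would narrow the interval at every later visit. Following C2 as written therefore gives less precise estimates than the collected data allow.

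The rest of the analysis is open. With no model and no missing-data method fixed in advance, the analyst can choose both after seeing the data, across two PROMIS domains and four postoperative visits. If dropout depends on earlier scores, comparisons restricted to those present at a visit can also be biased; a model that uses the earlier scores can address this under a missing-at-random assumption. At stake is the trial's whole secondary aim, with at most 25 patients per arm.

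**Working it through.** **Inputs**
- From G1: the sample size "is based upon a two-tail test at the 0.05 level of significance", "with 80% power to detect an effect size of" d = 0.8, 25 per arm; mean 149 mg, SD 37 mg.
- From F4: PROMIS SD of 10 points. This is the population norm; the SD in this trial's population is not given, so its use here is an assumption.
- Assumed, because the document gives no figure: correlation ρ between enrollment and follow-up score, 0.3 to 0.7; follow-up loss of 20% for illustration.

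**1. The plan's own figure (primary outcome)**
n per arm = 2 × (1.960 + 0.842)² / 0.8² = 24.5, so 25. The t-test version needs 25.5, so 26, and has power 0.791 at 25. The difference sought is 0.8 × 37 = 29.6 mg, and 29.6 / 149 = 19.9%. The stated figure reproduces.

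**2. PROMIS at one visit, no baseline adjustment**
Two-sample t-test, two-sided 0.05, 80% power, 25 per arm: detectable effect 0.809 SD, so 0.809 × 10 = 8.1 points. The normal approximation gives (1.960 + 0.842) × 10 × √(2/25) = 7.9.

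**3. The same visit, with the enrollment score as covariate (ANCOVA)**
Residual SD = 10 × √(1 − ρ²). Detectable difference = unadjusted value × √(1 − ρ²). Equivalent unadjusted sample = 25 / (1 − ρ²). The one degree of freedom spent on the covariate is ignored.

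| ρ (assumed) | √(1 − ρ²) | Detectable, t | Detectable, normal | Equivalent n per arm |
|---|---|---|---|---|
| none | 1 | 8.1 | 7.9 | 25 |
| 0.3 | 0.954 | 7.7 | 7.6 | 27.5 |
| 0.5 | 0.866 | 7.0 | 6.9 | 33.3 |
| 0.7 | 0.714 | 5.8 | 5.7 | 49.0 |

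The detectable difference falls by about 5%, 13% and 29%.

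**4. With 20 per arm at the visit (20% missing)**
Unadjusted 0.909 × 10 = 9.1 points; at ρ = 0.5, 9.1 × 0.866 = 7.9. The same 20 patients per arm enter both figures, so the gain comes from the covariate alone. Nothing here measures what a mixed model recovers from partly observed patients, or the bias that it might remove.

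**The case against.** The strongest reply is that C2 is an aims section, not a method. To say that scores are compared at listed times would also fit a longitudinal model with contrasts at each visit, and G2 does promise regression models. F2 and F4 leave enrollment out of the times at which benefit is expected, so C2 may simply be listing assessment times. On that view the plan is incomplete rather than wrong.

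Much of this stands, and it rules out several stronger readings that a reader might infer:

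- **That the plan prescribes separate unadjusted tests at each visit.** This is the natural reading of C2, but no test is named.
- **That patients who miss a visit are dropped.** No such rule exists, and G2 leaves adjustment open. Even separate tests would omit a patient only at the missed visit: 25 × 0.95 = 23.75 to 25 × 0.80 = 20 per arm at an assumed 5% to 20% missing. Requiring all four visits, with independent missingness, would leave 25 × 0.95⁴ = 20.4 to 25 × 0.80⁴ = 10.2, but the document does not require that.
- **That SRS-22 is compared visit by visit.** It is only said to be completed at these times and used to assess quality of life.
- **That the plan forecasts substantial loss.** It allows for the possibility, gives no rate, and sets out retention steps.

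The size of the gain is also soft: it depends on an unknown correlation and is small at 0.3.

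What the reply does not remove is the gap. On either reading no baseline adjustment, repeated-measures model or missing-data method is specified, and the one sentence that tests the recovery hypothesis treats enrollment as a comparison time.

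**Conclusion.** The point holds as a gap in the specification of a secondary analysis. C2 puts the enrollment score to an uninformative use, and nothing in the document puts it to the useful one. On the assumptions above, adjustment lowers the detectable PROMIS difference from 8.1 points to between 7.7 and 5.8. The direction holds for any non-zero correlation apart from the trivial cost of one degree of freedom; the size does not, and the equivalence to about 33 per arm belongs to ρ = 0.5 only. The benefit for missing data is real in principle but unquantified.

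The change should be made, but it is not critical: the primary analysis and the sample size in G1 are unaffected.

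**What to change.** Amend C2 and write out the inferential stage in G2 as follows.

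- Report enrollment PROMIS and SRS-22 scores by arm descriptively, with no group test.
- For each of PROMIS Mobility and Pain Interference, fit one mixed model for repeated measures to the 6-week and 3-, 6- and 12-month scores, with enrollment score, arm, visit, arm-by-visit and baseline-by-visit.
- Say whether SRS-22 is to be compared between groups. If so, use the same model and state whether the total or the domain scores are analysed.
- Include all randomised patients with at least one follow-up score, analysed as randomised.
- Name one key visit for the treatment contrast; present the others as supportive.
- Use an unstructured covariance, and name in advance the simpler structure to be used if it does not converge with about 50 patients.
- State the missing-at-random assumption and prespecify a sensitivity analysis that departs from it.
- Replace the aim labels in E2, 2.c with those in the current list.

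The cost is SAP wording and standard SAS code. No new data, visits or patients are needed.
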